8.1.4. Strategy for Intercurrent (Post-Randomization) Events

No intercurrent events are expected, in addition to those defined as protocol deviations. Missing data will not be imputed, regardless of the reason.

8.1.5. Statistical Analyses / Methods

Details of the planned displays are provided in [Appendix 10: List of Data Displays](#) and will be based on GSK Data Standards and statistical principles.

Unless otherwise specified, endpoints / variables defined in Section 8.1.1 will be summarized using descriptive statistics, graphically presented (where appropriate) and listed.

Summary statistics (N, n, arithmetic mean, 95% CI of arithmetic mean, geometric mean, 95% CI of geometric mean, SD, SD of log data, between-subject geometric CVb, median, minimum, maximum, and CV) for non-transformed and ln-transformed plasma CAB PK concentration and parameter values (C_{max} , AUCs, C_{τ} , and C_{24}) will be summarized by treatment and period, as appropriate.

Plasma CAB PK concentrations collected during the follow-up phase will only be summarized by visit for participants who received both injection 1 and injection 2 for cohorts 1-4 and 4b, and for participants who received injection 1 for cohort 4h and 5. All follow-up phase concentrations will be included in the individual CAB plasma concentration-time plots by injection and in data listings.

A population PK analysis using non-linear mixed effects modelling software NONMEM (ICON; Hanover, MD) maybe performed with the emergent data from this study to select optimal dosage regimens using simulations such that 5th percentile trough concentrations are maintained above Phase 3 trough concentrations benchmark. This analysis will be described and reported in a separate document(s) from the RAP.

8.1.5.1. Statistical Methodology Specification

The following PK statistical analyses will only be performed if sufficient data is available (i.e., if participants have well defined plasma profiles).

Endpoint / Variables

 AUC(0-τ), C_{max}, and C_{τ} for CAB 400 mg/mL following CAB IM (gluteus medius or vastus lateralis) or SC dosing
Model Specification for Pairwise and Historical Comparisons

 Pairwise comparisons between cohorts receiving the same dose of CAB400 but via different administration routes of CAB 400 mg/mL geometric mean plasma C_{τ}, C_{max}, and plasma AUC(0-τ) for Cohorts 1, 2, 3, 4, 4b and 4h will be conducted, as specified in Section 5.1. Cross study comparisons of geometric mean plasma C_{τ} for Cohorts 1, 2, 3, 4, 4b and 4h, and Cohort 5 compared to historical CAB 200 mg/mL data will be conducted, as specified in Section 5.1. Following log transformation, PK parameters will be separately analyzed using a linear regression model with a fixed effect term for treatment, with allowance for unequal variances for each treatment group (using the repeated / group=treatment option in the MIXED procedure to model unequal variances and DDFM=KENWARDROGER option for adjusted degrees of freedom). Point estimates and corresponding 90% CIs will be constructed for the treatment differences. Point estimates and their 90% CIs will then be transformed back to provide point estimates and 90% CIs on the original scale.
Historical CAB 200 mg/mL Data

 Anonymized reference dataset(s) containing the historical PK data from the ATLAS [201585], FLAIR [201584], and ÉCLAIR [201120] studies will be used in the historical cross-study comparison analyses described above. For ATLAS and FLAIR, concentrations meeting the definition of 'evaluable' as defined in the study-specific RAPs (e.g., excluding samples collected outside the ± 4 days evaluable sample window) will be used.
Model Checking & Diagnostics

 Model assumptions will be applied, but appropriate adjustments may be made based on the data.
Model Results Presentation

 Statistical analysis by analysis of variance (ANOVA) will be presented in tabular format with geometric mean ratios and corresponding 90% CI for the comparisons mentioned above.

Endpoint / Variables

 AUC(0-τ) [AUC(0-4) for Cohort 5], C_{max}, and C_{τ} [C₄ for Cohort 5] for CAB 400 mg/mL following Injection 1 of CAB IM (gluteus medius or vastus lateralis) or SC dosing, as data permit
Model Specification for Dose Proportionality Assessment

 AUC(0-τ) [AUC(0-4) for Cohort 5], C_{max}, and C_{τ} [C₄ for Cohort 5] following Injection 1 for CAB 400 mg/mL will be assessed separately for dose proportionality by route (IM gluteal, SC abdomen, IM lateral thigh) using pooled data across cohorts (Part 1 and Part 2, but excluding cohort 4h), where applicable, and the following power model: $y = \alpha * \text{dose}^\beta$

where y denotes the PK parameter and α is an intercept term. Dose proportionality in this model equates to $\beta=1$. A point estimate and 90% CI will be derived for β. β will be estimated by regressing the \log_e-transformed PK parameter on \log_e dose ($\text{Log}_e(\text{PK parameter}) = \log_e(\alpha) + \beta * \log_e(\text{dose})$).
 
 A fixed effects power model will be fitted by restricted maximum likelihood (REML) using SAS Proc Mixed.
Model Checking & Diagnostics

 Model assumptions will be applied, but appropriate adjustments may be made based on the data.
Model Results Presentation

 Statistical analysis by power model will be presented in tabular format with point estimates and corresponding 90% CI.

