6.2.1. Dosage and Administration

All participants will be assigned treatment with Oral CAB 30 mg once daily for 4 weeks during the Oral Lead In phase. Regardless of treatment arm assignment, the investigator should instruct all participants on the importance of treatment adherence. Participants will be recruited to Cohort 1 first, then to Cohort 2 and followed by Cohort 3. In circumstances where recruitment to or dosing of a cohort is paused, participants may be recruited to subsequent cohorts and re-randomized (only prior to the injection phase), if deemed appropriate by the investigator and sponsor. Dosing is outlined in [Table 2](#) below.

Table 2 Dosage and Administration

Oral Lead-In	
OLI Days 1 to 28	Take 1 tablet CAB 30 mg once daily. Should be taken with or without a meal once daily at approximately the same time each day.
7-14 Day Washout Period (from Day 29)	
Part 1	
First Injection (Loading Dose)	
Cohort 1	Receive CAB 600 mg given as 1 x 1.5 mL CAB 400 mg/mL formulation or 600 mg as 1 x 3 mL CAB 200 mg/mL IM gluteal injection
Cohort 2	Receive CAB 600 mg given as 1 x 1.5 mL CAB 400 mg/mL formulation or 300 mg as 1 x 1.5 mL CAB 200 mg/mL subcutaneous abdominal injection
Cohort 3	Receive CAB 600 mg given as 1 x 1.5 mL CAB 400 mg/mL formulation or 600 mg as 1 x 3 mL CAB 200 mg/mL IM lateral thigh injection The STR agreed ⁹ : Receive CAB 400 mg given as 1 x 1 mL of CAB 400 mg/mL formulation or 400 mg as 1 x 2 mL CAB 200 mg/mL IM lateral thigh injection
Cohort 4	Optional cohort. Receive CAB 400 mg/mL formulation (to a maximum of 1200 mg/3 mL if given IM or 600 mg/1.5 mL if given SC) or matched volume of CAB 200 mg/mL formulation if SC, and matched dose if IM. Dose determination by STR

⁹ At their meeting on 22 December 2020, the STR agreed to reduce the dose of the first injection for remaining Cohort 3 participants based on interim PK data from Cohorts 1 and 2.

	The STR agreed ¹⁰ : Receive CAB 400 mg given as 1 x 1 mL CAB 400 mg/mL formulation or 400 mg as 1 x 2 mL CAB 200 mg/mL IM gluteal injection
Cohort 4b	Receive CAB 300 mg given as 1 x 0.75 mL CAB 400 mg/mL formulation subcutaneous abdominal injection ¹¹
Cohort 4h	Receive 5000 U of rHuPH20 followed by CAB 400 mg given as 1 x 1 mL CAB 400 mg/mL formulation or 1 x 2 mL CAB 200 mg/mL given as subcutaneously abdominal injection (sequential administration). ¹²
Second Injection (Week 4 ± 3 days, see Appendix 8 [Section 11.8] for permissible procedures during the COVID-19 pandemic)	

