8. STUDY ASSESSMENTS AND PROCEDURES

- Study procedures and their timing are summarized in the SoA.

If these assessments are scheduled for the same nominal time, THEN the assessments should occur in the following order:

- 12-lead ECG
- vital signs
- blood draws.
- Protocol waivers or exemptions are not allowed
- Immediate safety concerns should be discussed with the sponsor immediately upon occurrence or awareness to determine if the participant should continue or discontinue study intervention.
- Adherence to the study design requirements, including those specified in the SoA, is essential and required for study conduct.
- All screening evaluations must be completed and reviewed to confirm that potential participants meet all eligibility criteria. The investigator will maintain a screening log to record details of all participants screened and to confirm eligibility or record reasons for screening failure, as applicable.
- Procedures conducted as part of the participant's routine clinical management (e.g., blood count) and obtained before signing of ICF may be utilized for screening or baseline purposes provided the procedure met the protocol-specified criteria and was performed within the time frame defined in the SoA.
- The maximum amount of blood collected from each participant over the duration of the study, including any extra assessments that may be required, will not exceed 500 mL
- Repeat or unscheduled samples may be taken for safety reasons or for technical issues with the samples.
- In Cohort 4b, participants will receive a topical NSAID or a topical steroid (high potency) as per the randomization schedule. These will be applied on Day -1 through to Day 5 after each subcutaneous abdominal injection.

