C _τ	Trough concentrations (C _τ) Tau=24 hours for OLI Day 29 Tau is 4 weeks for Inj. Phase in Cohort 1-4, 4b, and 4h Tau is 12 weeks for Inj. Phase in cohort 5.	Day 29	For Injection 1 & 2 in Part 1 and Part 2
C _τ /D	Trough concentrations (C _τ)/Dose Tau=24 hours for OLI Day 29 Tau is 4 weeks for Inj. Phase in Cohort 1-4, 4b, and 4h Tau is 12 weeks for Inj. Phase in cohort 5.	Day 29	For Injection 1 & 2 in Part 1 and Part 2
C4 Cohort 5 only	Trough concentrations on Week 4	NA	For Injection 1 & 2 in Part 2
C24	Trough Concentrations on Day 2 (24 hour)	Day 1	
t _{1/2}	Terminal absorption elimination half-life will be calculated as: t _{1/2} = ln2 / KALA	NA	For Injection 1 (Cohort 4h) & 2 in Part 1 and Part 2.
KALA	Terminal absorption elimination rate constant, Long-acting	NA	For Injection 1 (Cohort 4h) & 2 in Part 1 and Part 2

NOTES:

- Additional parameters may be included as required.
- In addition to the PK parameters calculated based on the observed concentrations for the 2 participants from Cohort 3 who received a CAB400 - Inj. 1 400 mg IM Lateral Thigh. PK parameters adjusted to a 600 mg dose will be calculated for these participants as well. The adjustment will be performed using a 50% increase of the plasma PK parameters.

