8.1.2. Summary Measure

For PK concentrations and PK parameters: arithmetic mean, 95% confidence interval (CI) of arithmetic mean, geometric mean, 95% CI of geometric mean, SD, SD of log data, between-subject geometric coefficient of variation (CV_b), median, minimum, maximum, and coefficient of variation (CV), as appropriate.

For pairwise comparisons of AUC(0-τ), C_{max}, and C_τ (CAB 400 mg/mL) between cohorts: geometric mean ratio and corresponding 90% CI.

For cross study comparisons of C_{τ} to historical CAB 200 mg/mL data: geometric mean ratio and corresponding 90% CI.

For dose proportionality assessments of $AUC(0-\tau)$ [$AUC(0-4)$ for Cohort 5], C_{max} , and C_{τ} [C_4 for Cohort 5] following injection 1 for CAB 400 mg/mL (across all cohorts in Part 1 and Part 2, excluding cohort 4h) for each route: mean slope estimated from the power model and the corresponding 90% CI.

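### In the supportive dose-proportionality analysis, the SC slope cannot separate dose from the Cohort 4b topical treatment, and the lateral-thigh dose contrast depends on two participants

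*SAP*

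**What the plan says.** SAP 8.1.5.1 regresses log PK parameter on log dose, with an intercept and a slope β only. AUC, Cmax and trough after Injection 1 of CAB 400 mg/mL will be "assessed separately for dose proportionality by route (IM gluteal, SC abdomen, IM lateral thigh) using pooled data across cohorts", with Cohort 4h excluded and pooling only where applicable. SAP 8.1.2 gives the same scope: "across all cohorts in Part 1 and Part 2, excluding cohort 4h) for each route". The output is Table 3.7. "A point estimate and 90% CI will be derived for" β, and β = 1 means proportionality. No margin or decision rule is given.

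Three further places determine who enters each fit:

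- **Cohort 4b dose.** Protocol 6.2.1, first injection: "Receive CAB 300 mg given as 1 x 0.75 mL CAB 400 mg/mL formulation subcutaneous abdominal injection".
- **Cohort 4b co-treatment.** Protocol Section 8: "In Cohort 4b, participants will receive a topical NSAID or a topical steroid (high potency) as per the randomization schedule". Application runs from the day before each injection to Day 5.
- **Cohort 3 dose change.** The note to SAP 8.1.1.2 creates extra PK parameters, scaled up by 50% to represent 600 mg, "for the 2 participants from Cohort 3 who received a CAB400 - Inj. 1 400 mg IM Lateral Thigh".

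**The concern.** A power-model slope is read as the effect of dose. For SC, every 300 mg participant had an anti-inflammatory applied at the injection site and no 600 mg participant was planned to. Any effect of the topicals on local absorption would enter β in full. Nothing in the data could reveal it, because nobody received 300 mg SC without a topical. The planned Cohort 4b summaries by sequence and period (SAP 5.1) compare steroid with NSAID, not topical with none.

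For the lateral thigh, the whole dose contrast comes from two participants, yet a slope would stand in the same table beside the IM gluteal one. The SAP also does not say whether the observed or the 600 mg-adjusted values for those two enter the fit. The adjustment already assumes the answer the model is meant to estimate.

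At stake is a supportive statement about two of the three routes, with Table 3.7 scheduled for the Cohort 1-5 interim as well as the later deliveries.

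**Working it through.** **1. Check the method on the plan's own figure.** The documents give no precision for β. The nearest figure is protocol Table 4, Week 4, N = 15 against 579, log-SD 0.66079, with a stated 90% half-width of 0.28470.

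t(0.95, 592) × 0.66079 × √(1/15 + 1/579) = 1.6474 × 0.66079 × 0.26152 = 0.2847. This agrees, so the same t-based approach is used below.

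**2. Who enters the Injection 1 fits (SAP 5.1, protocol 6.2.1)**

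| Route | Cohorts and doses | Planned n on CAB 400 mg/mL |
|---|---|---|
| IM gluteal | Cohort 4, 400 mg; Cohort 1, 600 mg; Cohort 5, 800 mg | 18 / 18 / 20 |
| SC abdomen | Cohort 4b, 300 mg with topical; Cohort 2, 600 mg without | 24 / 18 |
| IM lateral thigh | Cohort 3, 400 mg and 600 mg | 2 / at most 16 |

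Cohort 4 adds nothing to SC because its first injection is IM gluteal. Evaluable numbers (protocol 10.2) are 15 in each of Cohorts 1-4, 18 in Cohort 4b and 16 in Cohort 5.

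**3. SC identifiability.** The design columns (intercept, ln dose, topical yes/no) have rank 2, not 3. With two dose levels,

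β̂ = [ln GM(600) − ln GM(300)] / ln 2.

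If topicals multiply exposure by r, ln GM(300) rises by ln r, so β̂ = β − ln(r)/ln 2:

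| Assumed r | Shift in β |
|---|---|
| 0.80 | +0.32 |
| 0.90 | +0.15 |
| 1.10 | −0.14 |
| 1.25 | −0.32 |

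These values of r are illustrations only.

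**4. SC precision.** Half-width = t × SD × √(1/n₁ + 1/n₂) / ln(dose ratio).

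- Planned (24, 18): 1.6839 × 0.66079 × 0.3118 / 0.6931 = 0.50.
- Evaluable (18, 15): 1.6955 × 0.66079 × 0.3496 / 0.6931 = 0.57.
- IM gluteal for comparison, three doses: 0.52 planned, 0.57 evaluable.

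SC is about as precise as gluteal.

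**5. Lateral thigh.** Dose ratio 1.5, ln 1.5 = 0.4055.

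- 2 against 16: 1.7459 × 0.66079 × 0.75 / 0.4055 = 2.13. An estimate of exactly 1 would have a 90% CI of about −1.1 to 3.1.
- 2 against 13 (15 evaluable): 2.19.
- At an assumed SD of 0.30: 0.97, giving a CI of about 0.03 to 1.97.
- Each of the two 400 mg participants has leverage 0.50. Moving one of them by one SD changes β by 0.5 × 0.66079 / 0.4055 = 0.81.

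**6. The 600 mg-adjusted values.** Entered as 600 mg, they leave no dose contrast. Entered as 400 mg, they raise the low-dose log mean by ln 1.5 and so lower β by ln 1.5 / ln 1.5 = 1.

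**The case against.** **This analysis decides nothing.** Dose proportionality is not among the protocol objectives or endpoints, is absent from protocol 10.4.2, tests no hypothesis and has no margin. Regimen selection is left to population PK simulation reported separately (SAP 8.1.5). This stands. A reader might infer that the defect reaches the primary comparisons or dose selection; no passage uses the slope for either.

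**The topical effect is hypothetical.** The topicals stop at Day 5, while trough is at Week 4 and AUC spans four weeks, and much Cohort 4b text is redacted. This also stands. A reader might infer that the SC slope is known to be biased. The documents support only that a bias could not be detected.

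**Cohort 4h was excluded and 4b kept.** It is tempting to call this inconsistent. The SAP gives no reason for excluding 4h, and rHuPH20 is used because it enhances dispersion of the co-injected drug, whereas the topicals are described as mitigation. The parallel is an inference, and the case does not need it.

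**The hedges cover it.** SAP 8.1.5.1 limits the analyses to applicable, sufficient data with well-defined plasma profiles. That would let the sponsor drop a row, but it sets no minimum per dose and does not address confounding. Complete data would leave both problems in place.

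**Up to 18 participants enter the thigh fit, and its wide interval would be visible.** True: the fit does not consist of two people. The dose contrast does depend on two, and the open question about adjusted values would not be visible.

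**Gluteal dose is confounded with cohort too.** Also true, but no planned local co-treatment differs across those cohorts, and there are three dose levels.

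**Conclusion.** The point holds as an improvement to a supportive analysis. The SC slope is not identifiable as a dose effect: it is interpretable only if r = 1, which the readable text neither states nor tests. The possible shift is −ln(r)/ln 2 with r unknown. Imprecision is not the SC complaint. The lateral-thigh slope is uninformative, with a half-width of about 2.1.

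The half-widths rest on the historical Week 4 trough SD of 0.66079. The documents give no SD for Cmax or AUC, so those intervals may be narrower; the thigh conclusion survives even at the assumed SD of 0.30.

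A reader might take the SAP schedule footnote mentioning topical placebo to mean that some Cohort 4b participants had no active topical. The readable text does not support that: Protocol Section 8 gives every participant an NSAID or a steroid, and the preference endpoint in SAP 7.5.3 compares those two.

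**What to change.** In SAP 8.1.2, 8.1.5.1 and Table 3.7:

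- **Power model:** limit it to IM gluteal (400, 600, 800 mg).
- **SC:** report no dose-proportionality slope. Give the dose-normalised Cohort 4b:Cohort 2 geometric mean ratio with 90% CI, labelled 'dose and topical treatment combined; not an estimate of dose proportionality'. This ratio equals 2^(1−β̂), so it carries the same aliasing. The gain is in what is concluded, not in new information.
- **Steroid against NSAID within Cohort 4b:** add it only at the unblinded Cohort 1-5 and end-of-study deliveries. At the Cohort 1-5 interim, SAP 3.2 and Section 4 keep Cohort 4b blinded to topical treatment and bar presentation by topical group.
- **Lateral thigh:** list the two 400 mg participants' observed dose-normalised values without a slope. State that the 600 mg-adjusted values do not enter any proportionality fit.

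Cost: SAP wording and one table shell. The SC and lateral-thigh slope rows are lost.

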10. APPENDICES

10.1. Appendix 1: Exclusions from Per Protocol Population

Instream and final analysis population reviews as per SOP 130050 are not planned for this study because it does not include a Per-Protocol population. Exclusions of subjects from any analysis populations will be determined and documented prior to the DBF.

PK samples collected outside the protocol defined time-windows and/or other protocol deviations will be reviewed by the study team to determine whether the sample will be excluded from PK analyses.

10.2. Appendix 2: Schedule of Activities

10.2.1. Protocol Defined Schedule of Events

Screening Period and Oral Lead-in Phase: All Cohorts

Study Period	Screening ¹		Oral Lead-in ⁸			Day 29	Early withdrawal ¹⁰	Washout Period
			Dosing Days 1-28					
Visit Window	Within 30 days of oral lead-in	Within 5 days of admission to the clinic	Day 1	Day 2	Day 14	Within 24 hours of the Day 28 last dose	EW	7 – 14 days ¹¹
Informed Consent	X							
Demographics	X							
Medical / Medication / Drug / Alcohol History	X							
Inclusion/Exclusion Criteria ²	X		X					
Height, Weight, BMI	X						X	
Physical Exam	X						X	
Vital Signs ³	X		X	X	X	X	X	
Triplicate 12-Lead ECG ³	X		X			X	X	
Drug / Alcohol Screen ⁴	X		X					
Pregnancy Test ^{3,4}	X		X		X	X	X	
Testing for SARS-CoV-2	X	X ⁵						
Hepatitis B, Hepatitis C Screening	X							
HIV Test	X							
Haematology with differential; Clinical Chemistry Tests; Urinalysis ^{3,4}	X		X	X	X	X	X	
Coagulation Tests	X					X	X	
Admit to clinic			X ^{4,5}					
Dispense Oral lead-in IP ⁶			X					
Administer oral CAB ⁶			X	X	X			
Provide dosing diary card			X					
Discharge from clinic				X				
Drug accountability/ pill count/review drug diary				X	X	X	X	
Blood plasma PK sampling ⁷			X	X	X	X	X	

Study Period	Screening ¹		Oral Lead-in ⁸			Day 29	Early withdrawal ¹⁰	Washout Period
			Dosing Days 1-28					
Visit Window	Within 30 days of oral lead-in	Within 5 days of admission to the clinic	Day 1	Day 2	Day 14	Within 24 hours of the Day 28 last dose	EW	7 – 14 days ¹¹
AE Assessment ⁸			X	X	X	X	X	
Concomitant Medication Review	X		X	X	X	X	X	
Genetic sample ⁹			X					

1. Screening may occur over more than one visit but within 30 days of the first dose in the oral lead in phase.
2. Eligibility criteria must be carefully assessed at the Screening visit and confirmed at the Day 1 Oral lead-in phase visit.
3. Prior to administering the first oral dose of CAB, study personnel must verify the following pre-dose assessments to be within normal limits prior to administration: vital signs, ECG, pregnancy test (negative; females of reproductive potential [FRP] only). The results of the Drug/Alcohol screen, haematology with differential, clinical chemistry tests and urinalysis on Day 1 are not required prior to administering the first oral dose of CAB but samples should be drawn/collected prior to CAB administration.
4. Participants may be admitted to the clinic before Day 1 of the Oral Lead-in Phase. They may have some assessments, such as drug/alcohol screen, pregnancy test and haematology/chemistry/urinalysis, done on the day before Day 1.
5. The second test for severe acute respiratory syndrome coronavirus 2 (SARS-CoV-2) should be performed within 5 days of admission (ideally within 24 hours), and negative results for both tests are required prior to dosing. Any new Phase I unit participating in this study will adhere to the following SARS-CoV-2 testing procedures. **Where SARS-CoV-2 is circulating in the community**, participants are admitted for the second test for SARS-CoV-2; prior to the second test result being known, they should follow strict infection control procedures (personal protective equipment (PPE)/social distancing) and should be isolated within an area of the unit to avoid exposure to COVID-19 negative participants. Once the second test result is a confirmed negative, they can be released into the unit and follow infection control practices as per unit guidance. **Where SARS-CoV-2 is NOT circulating in the community**, the second test for SARS-CoV-2 may be performed within 5 days of admission to the clinic, and if participants are not admitted, they will be advised to avoid exposure to COVID-19 and self-quarantine until entrance to the unit while awaiting final testing clearance. Sponsor approval is required for site(s) to adopt SARS-CoV-2 testing within 5 days of admission to the clinic if study participants do not remain and isolate within the unit until test results are known.
6. Randomization in Part 1 to occur on Day 1 prior to oral dosing (randomization in Part 2 to occur on Day 1 of the injection phase prior to the first injection). Oral CAB dosing Days 1 to 28. Day 1, Day 2, and Day 14 doses should be administered in the clinic. The tablet should be taken at approximately the same time each day.
7. PK sampling – On Day 1 (1 h, 2 h, 3 h, 4 h, and 6 h, and in addition for Cohort 5 and Cohort 6 [if conducted] at 8 h, and 12 h) and Day 2 PK between 20 h and 28 h post first oral dose. Day 14 is a pre-dose PK sample. Day 29 assessments should occur between 20 h and 28 h of the last dose on Day 28. A total of 8 PK samples (10 PK samples for Cohorts 5 and 6) will be collected during oral lead-in phase. Please refer to Protocol Section 8.5 for permitted PK window for OLI phase.
8. AE assessment will include a brief, symptom-directed physical exam as needed.
9. Genetic sample Day 1 collect the sample at the earliest convenient time after the first dose in the oral lead in phase.
10. If a participant is withdrawn prior to receiving the CAB LA injection, a follow-up/withdrawal visit should be scheduled 10-14 days after the last oral dose of CAB.
11. The washout period may be extended if deemed necessary by the investigator and sponsor.

CAB 400 mg/mL or CAB 200 mg/mL LA Injection Phase and Follow- up: Part 1 Cohorts 1-4

		Injection Phase												Follow-up Phase										
Injection 1	Within 7 and/or 5 days of admission to the clinic ³	Inj 1 Day 1				Inj 1 Day 2	Inj 1 Day 3	Inj 1 Day 5	Inj 1 Day 6	Inj 1 Day 7	Inj 1 Day 8	Inj 1 Day 10	Inj 1 Day 14	Inj 1 Day 17	Inj 1 Day 22	Inj 1 Day 28 – proceed to Inj 2 Day 1	Follow-up post last injection							
Injection 2	Within 7 and/or 5 days of admission to the clinic ³	Inj 2 Day 1				Inj 2 Day 2	Inj 2 Day 3	Inj 2 Day 5	Inj 2 Day 6	Inj 2 Day 7	Inj 2 Day 8	Inj 2 Day 10	Inj 2 Day 14	Inj 2 Day 17	Inj 2 Day 22	Inj 2 Day 28 – proceed to follow-up	Week 4/ Day 28	Week 8	Week 12	Week 20	Week 28	Week 36	Week 44	Week 52 /EW ¹
Procedures		Pre-dose ²	1 h	2 h	8 h	24 h																		
Permitted window for PK collection		Within 1 h prior to dosing	±15 min	±30 min	±1 h	±2 h	±2 h	±2 h	±2 h	±2 h	±2 h	±1 day	±1 day	±1 day			±3 days	±3 days	±3 days	±3 days	±3 days	±3 days	±3 days	±3 days
Interim Medical /Medication/ Drug / Alcohol History		X																						
Pregnancy Test ^{3,8}		X										X				X	X	X			X	X		X
12-Lead ECG		X		X																				
Testing for SARS-CoV-2	X ³									X ³														

CONFIDENTIAL

212482

		Injection Phase												Follow-up Phase												
Injection 1	Within 7 and/or 5 days of admission to the clinic ³	Inj 1 Day 1					Inj 1 Day 2	Inj 1 Day 3	Inj 1 Day 5	Inj 1 Day 6	Inj 1 Day 7	Inj 1 Day 8	Inj 1 Day 10	Inj 1 Day 14	Inj 1 Day 17	Inj 1 Day 22	Inj 1 Day 28 – proceed to Inj 2 Day 1	Follow-up post last injection								
Injection 2	Within 7 and/or 5 days of admission to the clinic ³	Inj 2 Day 1					Inj 2 Day 2	Inj 2 Day 3	Inj 2 Day 5	Inj 2 Day 6	Inj 2 Day 7	Inj 2 Day 8	Inj 2 Day 10	Inj 2 Day 14	Inj 2 Day 17	Inj 2 Day 22	Inj 2 Day 28 – proceed to follow-up	Week 4/ Day 28	Week 8	Week 12	Week 20	Week 28	Week 36	Week 44	Week 52 /EW ¹	
Procedures		Pre-dose ²	1 h	2 h	8 h	24 h																				
HIV Test ^{3,9}		X																X								X
Haematology; Clinical Chemistry; Urinalysis ³		X										X		X				X	X	X				X	X	X
Coagulation Tests ³		X																								X
Brief Physical Exam		X				X						X						X	X	X				X	X	X
Weight																		X								X
Vital Signs		X	X	X	X	X	X	X	X	X	X	X	X	X	X	X		X	X	X				X	X	X
Admit to clinic		X ³																								
Administer CAB 400 mg/mL or CAB 200 mg/mL LA ⁴		X																								

[figure not shown]
CONFIDENTIAL

212482

		Injection Phase												Follow-up Phase										
Injection 1	Within 7 and/or 5 days of admission to the clinic ³	Inj 1 Day 1				Inj 1 Day 2	Inj 1 Day 3	Inj 1 Day 5	Inj 1 Day 6	Inj 1 Day 7	Inj 1 Day 8	Inj 1 Day 10	Inj 1 Day 14	Inj 1 Day 17	Inj 1 Day 22	Inj 1 Day 28 – proceed to Inj 2 Day 1	Follow-up post last injection							
Injection 2	Within 7 and/or 5 days of admission to the clinic ³	Inj 2 Day 1				Inj 2 Day 2	Inj 2 Day 3	Inj 2 Day 5	Inj 2 Day 6	Inj 2 Day 7	Inj 2 Day 8	Inj 2 Day 10	Inj 2 Day 14	Inj 2 Day 17	Inj 2 Day 22	Inj 2 Day 28 – proceed to follow-up	Week 4/ Day 28	Week 8	Week 12	Week 20	Week 28	Week 36	Week 44	Week 52 /EW ¹
Procedures		Pre-dose ²	1 h	2 h	8 h	24 h																		
CCI																								
Provide diary card regarding injection site reactions		X																						
Discharge from the clinic										X														
Injection site reaction assessment ¹⁰			X	X	X	X	X	X	X	X	X	X	X	X	X		X	X	X	X	X	X	X	X
AE Assessment ⁶			X	X	X	X	X	X	X	X	X	X	X	X	X		X	X	X	X	X	X	X	X
Device deficiencies		X	X																					
Concomitant Medication Review			X	X	X	X	X	X	X	X	X	X	X	X	X		X	X	X	X	X	X	X	X

		Injection Phase														Follow-up Phase								
Injection 1	Within 7 and/or 5 days of admission to the clinic ³	Inj 1 Day 1				Inj 1 Day 2	Inj 1 Day 3	Inj 1 Day 5	Inj 1 Day 6	Inj 1 Day 7	Inj 1 Day 8	Inj 1 Day 10	Inj 1 Day 14	Inj 1 Day 17	Inj 1 Day 22	Inj 1 Day 28 – proceed to Inj 2 Day 1	Follow-up post last injection							
Injection 2	Within 7 and/or 5 days of admission to the clinic ³	Inj 2 Day 1				Inj 2 Day 2	Inj 2 Day 3	Inj 2 Day 5	Inj 2 Day 6	Inj 2 Day 7	Inj 2 Day 8	Inj 2 Day 10	Inj 2 Day 14	Inj 2 Day 17	Inj 2 Day 22	Inj 2 Day 28 – proceed to follow-up	Week 4/ Day 28	Week 8	Week 12	Week 20	Week 28	Week 36	Week 44	Week 52 /EW ¹
Procedures		Pre-dose ²	1 h	2 h	8 h	24 h																		
Blood plasma PK Sampling ⁷		X	X	X	X	X	X	X	X	X	X	X	X	X	X		X	X	X	X	X	X	X	X

- Participants will have PK monitoring up to and including Week 52 post last injection. Participants with undetectable CAB concentrations before this timepoint will be deemed to have completed follow up and return to the clinic for a last study visit at which activities specified for the Week 52/EW visit will be performed. Participants who withdraw from the study before week 52 post last injection will be asked to return to the site for a withdrawal visit.
- On Day 1, study personnel must verify the following pre-dose assessments to be within normal limits prior to injection: ECG, brief physical exam, vital signs, pregnancy test (negative; FRP only), AE assessment, and concomitant medication assessment. If a clinical abnormality, clinically significant AE, or prohibited medication that precludes injection is observed/recorded, the medical monitor must be contacted for further instruction.
- Participants may be admitted to the clinic before Injection 1 Day 1 and Injection 2 Day 1. Any new Phase I unit participating in this study will adhere to the following SARS-CoV-2 testing procedures. **Where SARS-CoV-2 is circulating in the community**, participants should have one SARS-CoV-2 test approximately 1 week prior to admission to the clinic. A second test would be done upon admission; prior to the test result being known, participants should follow strict infection control procedures (PPE/social distancing) and should be isolated within an area of the unit to avoid exposure to COVID-19 negative participants until the test result is known. Once the test result is a confirmed negative, they can be released into the unit and follow infection control practices as per unit guidance. Any new Phase I unit participating in this study will adhere to the following SARS-CoV-2 testing procedures. A further test will be done on Day 8 upon discharge from the clinic. **Where SARS-CoV-2 is NOT circulating in the community**, SARS-CoV-2 testing prior to dosing may be performed within 5 days of admission to the clinic, and if participants are not admitted, they will be advised to avoid exposure to COVID-19 and self-quarantine until entrance to the unit while awaiting final testing clearance. Sponsor approval is required for site(s) to adopt SARS-CoV-2 testing within 5 days of admission to the clinic if study participants do not remain and isolate within the unit until test results are known. A further test is NOT required on Day 8 upon discharge from the clinic. Participants may have some assessments, such as HIV test, drug/alcohol screen, pregnancy test, haematology/chemistry/urinalysis and coagulation tests, done on the day before Injection 1 Day 1 and Injection 2 Day 1.

4. CAB 400 mg/mL - injection 1 loading dose of 600 mg and injection 2 400 mg; Cohort 1 Q4WM IM- via gluteus medius, Cohort 2 Q4W SC and Cohort 3 Q4W IM – lateral thigh/vastus lateralis. Cohort 4 dose and dosing schedule determination by STR based upon data from cohorts 1-3 and historical CAB 200 mg/mL data. Active controls will be administered CAB 200 mg/mL formulation matched on dose or volume to the CAB 400 mg/mL participants in Cohorts 1 and 3 and Cohort 2, respectively.
